#### 7.9.2 Analysis of primary endpoint – continuation phase - betweentreatment difference in HbA1C – non inferiority test

The goal is to assess the non-inferiority in the mean Hba1c during the 12-week continuation phase period 2 in the Treatment MiniMed 780G BLE 2.0 system with the DS5 sensor in Auto Mode compared to Control MiniMed 780G System in Auto Mode. The between-treatment difference will be compared using the following hypotheses:

$$\begin{array}{l} H_0: \Delta HbA1c \geq 0.4\% \\ H_\alpha: \Delta HbA1c < 0.4\%. \end{array}$$

Where  $\Delta HbA1c$  is the difference of the average of HbA1c for Treatment MiniMed 780G BLE 2.0 system with the DS5 sensor in Auto Mode vs Control MiniMed 780G in Auto Mode at the end of the 12-week continuation phase period 2, will be assessed by using of mixed model adjusting by baseline value. It will be tested at the 0.025 (one-sided) significance level.

The 97.5% upper confidence limit of between-treatment difference will be calculated. If it is lower than 0.4%, the non-inferiority will be concluded.

#### 7.9.3 Analysis of study phase secondary endpoints

Descriptive summary statistics of the secondary endpoints will be presented stratified by treatment.

# 7.9.3.1 Between treatment difference in HbA1c – non inferiority test endpoints

The between-treatment difference in mean HbA1c at the end of each 12-week period will be assessed similarly to primary endpoint analysis, using repeated measures mixed model with period, randomization sequence, and treatment as fixed effects, and subject as the random effect.

The between-treatment difference will be compared using the following hypotheses:

$$\begin{array}{l} H_0: \Delta HbA1C \geq 0.4\% \\ H_\alpha: \Delta HbA1C < 0.4\%. \end{array}$$

Where  $\Delta HbA1c$  is the average of the cross-over differences in HbA1c at the end of 12-week period in Treatment 780G in Auto Mode vs HbA1c at the end of 12-week period Control MiniMed 780G System + SBL ( $HbA1C_{AHCL} - HbA1C_{SBL}$ ), and the test will be against at the 0.025 (one-sided) significance level.

CIP342 LENNY Statistical Analysis Plan	Form
Revision 2.0 Page 22 of 31	Mecttronic

The 97.5% upper confidence limit of between-treatment difference will be calculated. If it is lower than 0.4%, the non-inferiority will be concluded.

# 7.9.3.2 Between treatment difference in TIR (70-180 mg/dL) – superiority test

The between-treatment difference in the percentage of time that the sensor glucose measurement is in the target range, 70 to 180 mg/dL (3.9-10.0 mmol/L), during each 12-week period in the Treatment 780G in Auto Mode compared to Control MiniMed 780G in Manual Mode + SBL will be assessed for superiority using repeated measures mixed model with period, randomization sequence, and treatment as fixed effects, and subject as the random effect.

The between-treatment difference will be compared using the following hypotheses:

$$H_0: \Delta TIR \le 0\%$$
  
$$H_{\alpha}: \Delta TIR > 0\%.$$

the test will be against at the 0.025 (one-sided) significance level.

The 97.5% lower confidence limit of between-treatment difference will be calculated. If it is greater than 0%, the superiority will be concluded.

#### 7.9.3.3 Between treatment difference in HbA1c – superiority test

The between-treatment difference in mean HbA1c at the end of each 12-week period will be assessed for superiority using repeated measures mixed model with period, randomization sequence, and treatment as fixed effects, and subject as the random effect.

The between-treatment difference will be compared using the following hypotheses:

$$\begin{split} H_0: \Delta H b A 1 C &\geq 0\% \\ H_\alpha: \Delta H b A 1 C &< 0\%. \end{split}$$

the test will be against at the 0.025 (one-sided) significance level.

The 97.5% upper confidence limit of between-treatment difference will be calculated. If it is lower than 0%, the superiority will be concluded.

#### 7.9.4 Analysis of continuation phase secondary endpoints

Descriptive summary statistics of the secondary endpoints will be presented stratified by treatment.

CIP342 LENNY Statistical Analysis Plan	Form	
Revision 2.0	Page 23 of 31	Mecttronic

#### **7.9.4.1** Between treatment difference in HbA1c – superiority test endpoints

The between-treatment difference in mean HbA1c of the 12-week continuation phase period 2 will be assessed similarly to primary endpoint analysis, using mixed model adjusting by baseline value. The between-treatment difference will be compared using the following hypotheses:

$$H_0: \Delta HbA1C \ge 0\%$$
  
$$H_{\alpha}: \Delta HbA1C < 0\%.$$

Where  $\Delta HbA1c$  is the difference of the average of HbA1c for Treatment MiniMed 780G BLE 2.0 system with the DS5 sensor in Auto Mode vs Control MiniMed 780G in Auto Mode at the end of the 12-week continuation phase period 2, and the test will be against at the 0.025 (one-sided) significance level.

The 97.5% upper confidence limit of between-treatment difference will be calculated. If it is lower than 0%, the superiority will be concluded.

# 7.9.4.2 Between treatment difference in TIR (70-180 mg/dL) – non inferiority-test

The between-treatment difference in the percentage of time that the sensor glucose measurement is in the target range, 70 to 180 mg/dL (3.9-10.0 mmol/L), during the 12-week continuation phase period 2 in the Treatment MiniMed 780G BLE 2.0 system with the DS5 sensor in Auto Mode vs Control MiniMed 780G in Auto Mode will be assessed for non-inferiority using mixed model adjusting by baseline value.

The between-treatment difference will be compared using the following hypotheses:

$$\begin{aligned} H_0: \Delta TIR &\leq -7.5\% \\ H_\alpha: \Delta TIR > -7.5\%. \end{aligned}$$

Where  $\Delta TIR$  is the difference in time in range in Treatment MiniMed 780G BLE 2.0 system with the DS5 sensor in Auto Mode vs Control MiniMed 780G in Auto Mode , and the test will be against at the 0.025 (one-sided) significance level.

The 97.5% lower confidence limit of between-treatment difference will be calculated. If it is greater than -7.5%, the non-inferiority will be concluded.

CIP342 LENNY Statistical Analysis Plan		Form
Revision 2.0 Pa	ige 24 of 31	Medtronic

#### 7.9.4.3 Between treatment difference in TIR (70-180 mg/dL) – superiority test

The between-treatment difference in the percentage of time that the sensor glucose measurement is in the target range, 70 to 180 mg/dL (3.9-10.0 mmol/L), during the 12-week continuation phase period 2 in the Treatment MiniMed 780G BLE 2.0 system with the DS5 sensor in Auto Mode vs Control MiniMed 780G in Auto Mode will be assessed for superiority using mixed model adjusting by baseline value.

The between-treatment difference will be compared using the following hypotheses:

$$H_0: \Delta TIR \leq 0\%$$
  
$$H_{\alpha}: \Delta TIR > 0\%.$$

Where  $\Delta TIR$  is the difference in time in range in Treatment MiniMed 780G BLE 2.0 system with the DS5 sensor in Auto Mode vs Control MiniMed 780G in Auto Mode , and the test will be against at the 0.025 (one-sided) significance level.

The 97.5% lower confidence limit of between-treatment difference will be calculated. If it is greater than 0%, the non-inferiority will be concluded.

This document is electronically controlled

CONFIDENTIAL

This document is electronically controlled *Medtronic Business Restricted* 056-F286, Statistical Analysis Plan Template Rev C

This document is electronically controlled

CIP342 LENNY Statistica	I Analy	ysis Plan		Form
Re	evision	2.0	Page 27 of 31	Mectronic
			I	
		I		

This document is electronically controlled

CIP342 LENNY Statistical	Analy	ysis Pla	an	Form
Re	vision	2.0	Page 28 of 31	Medtronic
			l	

## 7.10 Safety Evaluation

The safety endpoints will be assessed separately for the study phase and continuation phase of the study. For study phase the events will be reported for each period (Run-In, Study phase period 1, washout period, study period 2). For the continuation phase the events will be reported for each period (Run-in 2, continuation phase period 1 and continuation phase period 2). For study and continuation phases events will be reported by both randomization arm and actual treatment received and will be presented for the Safety population.

CIP342 LENNY Statistical Analysis Plan	Form
Revision 2.0 Page 29 of 31	Medtronic

Any safety related event will be classified by study period according to the rule defined in paragraph 7.2.

The listing of these events will also be reported.

#### 7.10.1 Number of severe hypoglycemic events

Severe Hypoglycemia is an event requiring assistance of another person due to altered consciousness to actively administer carbohydrate, glucagon, or other resuscitative actions. This means that the subject was impaired cognitively to the point that he/she was unable to treat him or herself, was unable to verbalize his or her needs, and was incoherent, disoriented and/or combative. These episodes may be associated with sufficient neuroglycopenia to induce seizure or coma. Plasma glucose measurements may not be available during such an event, but neurological recovery attributable to the restoration of plasma glucose to normal is considered sufficient evidence that the event was induced by a low plasma glucose concentration.

Total number of severe hypoglycemic events will be reported by treatment.

The number of severe hypoglycemic events per year will be computed for each subject based on the entire study phase duration. If a subject i is followed up for xi years and the number of observed severe hypoglycemic events during that follow up is mi, the number of severe hypoglycemic events per year (SHEyear) for patient i will be estimated as:

$$\frac{m_i}{x_i}$$

Annualized crude incidence rates will be expressed as number of severe hypoglycemic events per 100 patients' year and will be calculated as:

$$\frac{\sum_{i=1}^{n} m_i}{\sum_{i=1}^{n} x_i} \times 100$$

where i=1, 2, ..., n and n total number of subjects.

The number of severe hypoglycemic events per 100 patients' year during the study phase will be reported by treatment.

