# 4.3 Safety Endpoints

The following safety endpoints will be assessed for each treatment during each 12-week period in both the study phase and continuation phase:

- Number of severe hypoglycemic events
- Number of Diabetic Ketoacidosis events (DKA)
- Number of Serious Adverse Events (SAEs)
- Number of Serious Adverse Device Events (SADEs)
- Number of Unanticipated Serious Adverse Device Events (USADEs)
- Number of Device Deficiencies for each treatment during each 12-week period in the Study Phase

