#### Study Phase:

During the study phase, each sequence consists of 2 phases of 12 weeks each separated by a 2-week washout phase for a total of 26 weeks.

- Sequence A: subjects will start using the MiniMed 780G system in Auto Mode for 12 weeks (Treatment). The washout phase of 2 weeks will be followed by a 12-week phase where subjects will use 780G system in Manual Mode with SBL activated (Control).
- Sequence B: subjects will continue to use MiniMed 780G system in Manual Mode with SBL activated for 12 weeks (Control). After a washout phase of 2 weeks, subjects will start to use the MiniMed 780G system in Auto Mode for a 12-week phase (Treatment).

During the washout period all the subjects will use MiniMed 780G system in Manual Mode with SBL activated.

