#### 7.7.1 Study exposure for Study Phase

For study phase, the Run-In phase starts at Visit 2, and it ends at the time of randomization. It is expected that the Run-In phase will last 2 to 4 weeks.

The Study phase starts at the time of Randomization (end of Run-In phase), and it ends at Visit 11.

The study phases exposures are calculated as:

- Study phase exposure (days) = (Visit 11 date (or study exit date, if early exited) date of Randomization +1).
- Run-In phase exposure (days) = (date of Randomization (or study exit date, if early exited) Visit date) +1).
- Pre-Run-In phase exposure (days) = (Visit 2 date of Enrollment (Consent) +1).

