#### 7.7.2 Study exposure for Continuation Phase

For continuation phase, the Run-In, in case of newly enrolled patients, starts at Visit 2A, and it ends at Visit 3A. It is expected that the Run-In phase will last around 10 days.

The Continuation phase starts at Visit 11, and it ends at Visit 15.

The continuation phases exposures are calculated as:

- Continuation phase exposure (days) = Visit 15 date (or study exit date, if early exited) Visit 11 date (or Visit 3A for newly enrolled patients, if any) +1).
- Run-In phase exposure (days) = Visit 12 date Visit 2A date +1.
- Pre-Run-In phase exposure (days) = Visit 2A Visit 1A +1.
- Continuation phase period 1 exposure (days) = Visit 13 date (or study exit date, if early exited) Visit 11 date (or Visit 3A for newly enrolled patients, if any) +1.
- Continuation phase period 2 exposure (days) = Visit 15 date (or study exit date, if early exited) Visit 13 date +1.

Extent of study exposures will be presented in a summary table.

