#### 7.10.2 Number of diabetic ketoacidosis events

A diabetic ketoacidosis event is defined as an event of blood glucose greater than 250 mg/dL (13.9 mmol/L) arterial pH less than 7.3, bicarbonate less than 15mEq/l, moderate ketonuria or ketonemia, and requiring treatment within a health care facility.

CIP342 LENNY Statistical Analysis Plan	Form
Revision 2.0 Page 30 of 31	Medtronic

Total number of diabetic ketoacidosis events will be reported by treatment. The number of diabetic ketoacidosis events per 100 patients' year during the study phase will be calculated in a similar way as in section 7.10.1 and will be reported by treatment.

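### The by-treatment severe-hypoglycaemia and DKA rates take their follow-up time from the whole crossover phase; read literally, each comes out at about 46% of its on-treatment value

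*SAP*

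**What the plan says.** SAP 7.10.1 sets the time base first: "The number of severe hypoglycemic events per year will be computed for each subject based on the entire study phase duration". Each child has x_i years of follow-up, and "the number of observed severe hypoglycemic events during that follow up is mi". The pooled rate is 100 times the sum of m_i over the sum of x_i, taken over all n subjects. Neither symbol carries a treatment or period index. The section closes by saying that the rate per 100 patients' "year during the study phase will be reported by treatment". For DKA, SAP 7.10.2 says that the rate "will be calculated in a similar way as in section 7.10.1 and will be reported by treatment".

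SAP 7.7.1 defines one exposure from randomization onwards, which starts "Study phase exposure (days) = (Visit 11 date (or study exit date, if early exited" and subtracts the randomization date, plus one day. It gives no exposure by period or by treatment. SAP 7.7.2 does so for the continuation phase, for example "Continuation phase period 1 exposure (days) = Visit 13 date (or study exit date, if early exited".

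Other sections look at the phase in pieces. SAP 4.3 says that "safety endpoints will be assessed for each treatment during each 12-week period in both the study phase and continuation phase". SAP 7.2 gives period 1, washout and period 2 separate windows for safety events, and SAP 7.10 reports events by those periods and also by actual treatment received. On washout, SAP 5 says: "During the washout period all the subjects will use MiniMed 780G system in Manual Mode with SBL activated".

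**The concern.** Every child who completes the study phase contributes Auto Mode time, Control time and washout time. The length of the whole phase therefore cannot be the person-time at risk on either treatment. If Auto Mode events are divided by whole-phase time, and Control events likewise, both rates are diluted by days on which the child was not using that treatment.

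At stake are the absolute rates of severe hypoglycaemia and DKA in children aged 2 to 6, in a trial whose stated purpose includes demonstrating safety. Rates per 100 patient-years invite comparison with rates from elsewhere, and a figure less than half its proper size would look reassuring for no good reason. The SAP also requires double programming of all outputs (section 8). Two programmers working from this text could choose different denominators and both defend the choice.

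**Working it through.** **Inputs.** Protocol 9.1: Visit 7 is Visit 3 + 84 days (±5); Visit 8 is Visit 7 + 14 days (up to +3); Visit 11 is Visit 7 + 98 days (±5). For Sequence A, Auto Mode starts at Visit 3A, which is Visit 3 + 0 to 3 days with up to 2 more. SAP 7.2: safety windows. SAP 7.7.1: exposure formula. Protocol synopsis: about 80 randomized, 72 completing the study phase.

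**1. The plan's own length.** 84 + 98 = 182 days = 26 weeks, as SAP 5 states. The SAP 7.7.1 formula adds one day: 183.

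**2. Days in each SAP 7.2 safety window at target visits.**
- Period 1 (Visit 3 to Visit 7, both included): 84 + 1 = 85
- Washout (both ends excluded): 14 − 1 = 13
- Period 2 (Visit 8 included, Visit 11 excluded): 98 − 14 = 84

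These sum to 182. The one-day gap to 183 is the day of Visit 11, which SAP 7.7.1 counts and the SAP 7.2 window does not.

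**3. Literal rate against on-treatment rate.** Averaged over the two sequences, each treatment has (85 + 84)/2 = 84.5 days. With the same events in the numerator, literal rate / on-treatment rate = 84.5/183 = 0.462. In weeks, 12/26 = 0.462.

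**4. Range for one child within the visit windows.**
- Lowest: period 2 with Visit 7 at day 89, Visit 8 at +17 and Visit 11 at +93 gives (93 − 17)/(89 + 93 + 1) = 76/183 = 0.415.
- Highest: period 1 with the same Visit 7 and Visit 11 gives 90/183 = 0.492.

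**5. Illustration (assumed: 2 events on one treatment, 80 children, all complete).**
- On-treatment: 2/(80 × 84.5/365.25) × 100 = 10.8 per 100 patient-years
- Literal: 2/(80 × 183/365.25) × 100 = 5.0 per 100 patient-years

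**6. Effect on the ratio.** With a shared denominator the reported Auto/Control ratio is m_A/m_C. The on-treatment ratio is (m_A/x_A)/(m_C/x_C). The reported ratio is therefore the on-treatment ratio times x_A/x_C.
- Completers, equal sequences: 84.5/84.5 = 1, so no distortion.
- Assumed extreme: 40 children per sequence, and all 8 non-completers leave one sequence at Visit 7. If they are in Sequence A, x_A = 40 × 85 + 40 × 84 = 6,760 days and x_C = 32 × 84 + 40 × 85 = 6,088 days, a factor of 1.11. If they are in Sequence B, the factor is 6,088/6,760 = 0.90. Exits spread evenly over the sequences bring it back towards 1.

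**7. Actual mode.** SAP 7.2 starts period 1 at Visit 3, but Sequence A may start Auto Mode up to 3 + 2 = 5 days later. Sequence A then has 80 to 85 Auto Mode days at target visits, and the two-sequence mean is (80 + 84)/2 = 82 to 84.5 days. By actual mode the Auto Mode share is 82/183 = 0.448 to 0.462.

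**8. Separate check of run-in 2 in SAP 7.7.2.** The text ends run-in 2 at Visit 3A; the formula ends it at Visit 12. At target dates Visit 2A is Visit 1A + 0 to 3 days, Visit 3A is Visit 2A + 7 and Visit 12 is Visit 1A + 42.
- Formula as written: 42 − (0 to 3) + 1 = 40 to 43 days
- Ending at Visit 3A: 7 + 1 = 8 days
- For new enrollees continuation period 1 exposure starts at Visit 3A, so 42 − (7 to 10) + 1 = 33 to 36 days are counted in both.

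**The case against.** The best defence is that a competent analyst would get this right. The sentence naming the whole phase describes a per-child statistic, for which whole-phase follow-up is coherent; the by-treatment rate comes later. Because m_i is defined over the same follow-up as x_i, restricting events to a treatment should restrict time as well. SAP 4.3 and the SAP 7.2 windows point the same way, and the table templates, kept in a separate document, may state the denominators. This reading is sound, and on it there is no material error. But it is not written down: the pooled formula reuses x_i unchanged, and the only duration named is the whole phase.

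A reader might go further and infer that washout will be counted as Control, since children use the same mode in both, so that the comparison between modes is biased. The documents do not support that. SAP 5 and Protocol 9.4.1 attach Control to the 12-week periods, SAP 4.3 assesses each treatment in each 12-week period, and SAP 7.2 and 7.10 give washout its own window and its own reporting period. Only the table by actual treatment received leaves the place of washout open. That wording came in with SAP version 2.0, together with the per-protocol exclusion for non-compliance with the assigned treatment. This suggests that it is aimed at children on the wrong treatment, not at washout.

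**Conclusion.** The point holds as a minor defect of specification. Followed literally, SAP 7.10.1 and 7.10.2 put each by-treatment rate at about 46% of its on-treatment value at target visits (about 42% to 49% for one child within the visit windows). The Auto/Control ratio is unchanged for completers in equal sequences. Early exits can move it, by a factor of about 0.90 to 1.11 in the assumed extreme where all 8 expected non-completers leave one sequence at Visit 7.

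The 46% rests on target visit dates and on events being counted within the SAP 7.2 windows. The event count in the illustration is assumed, because the documents give no expected rate. Nothing beyond these descriptive rates is touched: counts by treatment and by period and the listings stand, and SAP 7.5 plans no statistical test on safety endpoints. The run-in 2 formula is a separate internal contradiction. It adds no weight here and matters only if continuation enrolment reopens.

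**What to change.** - **SAP 7.10.1 and 7.10.2:** for the by-treatment rates, define m_i and x_i for each child within each treatment's own 12-week period, using the SAP 7.2 safety windows. Early exits contribute only their days on that treatment. The rate is 100 times the sum of m over the sum of x within treatment. Report washout events and person-time separately, as SAP 7.2 and 7.10 already do for events.
- **Table by actual treatment:** use actual mode dates, because Sequence A may start Auto Mode at Visit 3A. State how washout is treated, and treat it the same way in numerator and denominator.
- **SAP 7.7.1:** add exposure formulas for period 1, washout and period 2, matching the per-period formulas in SAP 7.7.2, and make the handling of the Visit 11 day agree with SAP 7.2.
- **SAP 7.7.2 (separate):** end run-in 2 exposure at Visit 3A, as the section's own text says.

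The cost is a few sentences and a small programming change. The visit dates are already collected and the windows already exist. If the table templates already state denominators, they need only be brought into line.

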12.2 Data Monitoring Committee

A Data Monitoring Committee (DMC) consisting of external physicians with an expertise in Endocrinology and the management of insulin-requiring diabetes including pump and CGM therapy, will be convened to review study progress and safety. The board will convene periodically. The DMC Charter is available under a separate cover.

The DMC will perform 2 main functions:

First: DMC will track and trend the overall safety of the study.

Event rate, defined as number of events per 100 patient years will be reviewed by the DMC with respect to the following:

• Event rate of all SAE
D00674412

- Event rate of severe hypoglycemia
- Event rate of DKA
- Event rate of device related AE

Second: Based on their meeting, DMC will recommend a decision to the sponsor regarding the following:

- Whether or not enrollment should be halted.
- Whether or not the entire study will need to be stopped including for those subjects who have received study devices already.

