#### 7.10.3 Number of Serious Adverse Events (SAEs), Serious Adverse Device Effects (SADEs), Unanticipated Serious Adverse Device Effects (USADEs) and Device Deficiencies (DD)

Serious Adverse Event (SAE) is an adverse event that led to any of the following:

- a) death,
- b) serious deterioration in the health of the subject, users, or other persons as defined by one or more of the following:
  - 1. a life-threatening illness or injury, or
  - 2. a permanent impairment of a body structure or a body function including chronic diseases, or
  - 3. in-patient or prolonged hospitalization, or
  - 4. medical or surgical intervention to prevent life-threatening illness or injury or permanent impairment to a body structure or a body function,
- c) foetal distress, foetal death or a congenital abnormality or birth defect including physical or mental impairment.

Serious Adverse Device Effect (SADE) is an adverse device effect that has resulted in any of the consequences characteristic of a serious adverse event.

Unanticipated Serious Adverse Device Effect (USADE) is a serious adverse device effect which by its nature, incidence, severity, or outcome has not been identified in the current risk assessment.

Device deficiency (DD) is inadequacy of a medical device with respect to its identity, quality, durability, reliability, usability, safety, or performance. It includes malfunctions, use errors, and inadequacy in the information supplied by the manufacturer including labelling. This definition includes device deficiencies related to the investigational medical device or the comparator.

The number of SAE, SADE, USADE and DD will be reported by study period and treatment.

The listing of these events will also be reported.

CIP342 LENNY Statistical Analysis Plan		Form
Revision 2.0	Page 31 of 31	Mecttronic

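### Severe-hypoglycaemia and DKA rates are planned for the study phase only and without intervals, so the BLE 2.0 pump and DS5 sensor get event counts not linked to exposure

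*SAP*

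**What the plan says.** SAP 7.10.1 defines a crude annualised rate: total events divided by total follow-up years, times 100. It limits the scope: the severe-hypoglycaemia rate per 100 patient-years "during the study phase will be reported by treatment". The per-subject version "will be computed for each subject based on the entire study phase duration". SAP 7.10.2 follows for DKA: "The number of diabetic ketoacidosis events per 100 patients' year during the study phase will be calculated in a similar way". No interval is attached to either rate.

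For the remaining safety endpoints, SAP 7.10.3 plans counts: "The number of SAE, SADE, USADE and DD will be reported by study period and treatment". SAP 7.10 sets the grouping: "For study and continuation phases events will be reported by both randomization arm and actual treatment received". Protocol 14.5.5 also plans totals and listings only.

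The parts needed for a continuation-phase rate are already present. SAP 7.7.2 derives period-2 follow-up ("Continuation phase period 2 exposure (days) = Visit 15 date (or study exit date, if early exited", less the Visit 13 date) and puts exposure in a summary table. Protocol 12.2 uses rates for monitoring: "Event rate, defined as number of events per 100 patient years will be reviewed by the DMC", with no limit to one phase.

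**The concern.** SAP 4.3 sets the safety endpoints for each treatment in each 12-week period of both phases, but the rate method covers only one phase. The phase left out is the one in which arm A2 uses the pump and sensor that are not CE-marked. The protocol's purpose is to demonstrate safety, and the objective in SAP 4.1 extends the safety evaluation to the new system.

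Two things are at stake. First, with so little follow-up, a count of zero or one is easily read as reassurance when it excludes little. Second, a count without its denominator is a poor comparison when follow-up differs between groups. Early exits cause that in the randomised arms. In the groups by treatment received, which SAP 2.0 added, nothing in the design makes the sizes equal.

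**Working it through.** **The plan's own figure.** Protocol 8.1 and 14.6.1 give about 72 study-phase and 64 continuation-phase completers, and the synopsis gives about 80 randomised. With 10% loss in each phase: 80 × 0.90 = 72, and 72 × 0.90 = 64.8, against the stated 64. The figure reproduces. Allocation at Visit 13 is 1:1 (Protocol 9.4.2), so 64 / 2 = 32 per arm.

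**Exposure.** Patient-years = children × 84 days / 365.25, assuming full 12-week follow-up.

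**Interval.** For m events in T patient-years, the exact two-sided 95% Poisson limits per 100 patient-years are:
- lower = 100 × χ²(0.025; 2m) / (2T), or 0 if m = 0
- upper = 100 × χ²(0.975; 2m + 2) / (2T)

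For m = 0 the upper limit is 100 × 3.689 / T.

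| Setting | Children | Patient-years | Upper limit, 0 events | 1 event: rate (95% CI) |
|---|---|---|---|---|
| Period 2, per arm, planned completers | 32 | 7.36 | 50.1 | 13.6 (0.3 to 75.7) |
| Period 2, per arm, if all 72 study-phase completers are randomised | 36 | 8.28 | 44.6 | 12.1 (0.3 to 67.3) |
| Period 2, per arm, if 40 are exposed | 40 | 9.20 | 40.1 | 10.9 (0.3 to 60.6) |
| Study phase, per treatment, planned completers | 72 | 16.56 | 22.3 | 6.0 (0.2 to 33.6) |

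**What a zero would mean.** Suppose the true rate on the new system were 20 per 100 patient-years. This value is chosen for illustration; the documents give none. The chance of seeing no event in 7.36 patient-years is exp(−0.20 × 7.36) = 0.23.

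**The study-phase denominator.** SAP 7.7.1 derives one study-phase exposure, from randomisation to Visit 11. On schedule that is 84 + 98 = 182 days, covering both treatments and the washout. A by-treatment rate should use about 84 days per child. If the 182-day figure were used for each treatment, 72 children would give 72 × 182 / 365.25 = 35.88 patient-years, and one event would show as 100 / 35.88 = 2.8 per 100 patient-years instead of 6.0. That factor is 84 / 182 = 0.46. The SAP does not say which denominator the by-treatment rate uses.

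**The case against.** The best defence is that the plan does what its endpoint asks. Protocol 4.4 and SAP 4.3 define the safety endpoints as numbers of events, so the study-phase rates go beyond the definition. SAP 7.5.2 rules out tests on safety endpoints, and the formal claim for the new system rests on HbA1c. Safety is descriptive, with listings, adjudication by the clinical events committee, and rates reviewed by the DMC. SAP 7.2 has a general two-sided 95% interval rule that could be read to cover rates, and the table templates are in a separate document not available here. All of this stands, and it keeps the point minor. It does not close the gap. The general rule does not commit to intervals on safety rates, DMC monitoring is not the final report, and an interval is estimation, so it does not conflict with the ban on tests.

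Four stronger readings are tempting, and the documents do not support them:
- **The new system is assessed only by treatment received.** SAP 7.10 also reports by randomised arm.
- **Exposure is ignored.** SAP 7.7.2 derives and tabulates it. What is missing is a link to the counts, and the text does not say the table is split by arm.
- **The new system's safety is decided on raw counts.** No decision rule uses these events.
- **Counts by treatment received will be distorted by a known amount.** If 4 of 36 children assigned to A2 stayed on the 780G, the groups would be 32 and 40, and equal true rates would give 40 / 32 = 1.25 times the expected events on the 780G. The documents give no number of children who switched, and at zero or one event such a ratio would hardly be visible.

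**Conclusion.** The concern holds as a limited reporting gap. The text restricts the severe-hypoglycaemia and DKA rates to the study phase and names no interval. Continuation period 2 therefore has counts and listings without a planned rate or measure of precision.

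At zero events, the upper limit that would go unreported is about 50 per 100 patient-years per arm in period 2 (40 to 45 if 36 to 40 per arm are exposed) and about 22 per treatment in the study phase. These figures assume equal arms, full 84-day follow-up and a constant Poisson rate. Early exits would raise the limits. Any added enrolment after the sample-size re-estimation would lower them; the documents do not give its size. The pages left blank before SAP 7.10 in the public copy are not relied on.

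The undefined by-treatment denominator should be settled at the same time, because extending the present wording would carry it into the continuation phase. No endpoint, error rate or efficacy conclusion is affected.

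**What to change.** Amend SAP 7.10.1 and 7.10.2 as follows:

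1. Report severe-hypoglycaemia and DKA rates per 100 patient-years for continuation period 2 as well. By randomised arm, use the period-2 exposure from SAP 7.7.2. By actual treatment, use person-time on the device actually worn, because the Visit 13 to Visit 15 exposure does not separate devices for a child who changes during the period.
2. For study-phase rates by treatment, use person-time in that treatment's own period, with the safety windows in SAP 7.2, in place of the whole study-phase duration.
3. Print patient-years beside each count, and give an exact Poisson two-sided 95% interval for every severe-hypoglycaemia and DKA rate in both phases.

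The cost is a few sentences and a few more table cells, plus deriving time on each device for any child who changed system. No new visits are needed. The drawback is that the intervals will be wide and will limit how strongly safety can be worded.
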